Hypothesis 2A. Specialized care delivered through a stepped care management program plus prospective PA will be associated with statistically significantly lower rates of unsafe opioid prescribing and improved patient outcomes compared to patients receiving usual care and PA only.

Specific aim 3. Using qualitative methods, identify key environmental, programmatic and policy factors that influenced the design, implementation and impact of the PA program in WA and the RR program in OH. This information will lead to the development of an Opioid Review Tool educational module for dissemination to both public and private payers.

3. Study Design

Study type: Observational cohort study, with prospective and retrospective components. Aims 1 and 2 rely primarily on administrative data for a prospective cohort, with longitudinal surveys conducted among a subset of the cohort. Aim 1 also includes a retrospective time series analysis. Aim 3 relies on qualitative research, including individual in-depth interviews and key informant interviews.

4. Study Population and Sample

Study Population and Setting

Workers' Compensation (WC). WC provides no-fault industrial insurance coverage for most employers and workers in WA and OH. Benefits include medical treatment for workers who are injured or develop an occupational disease as a result of their work activities. Workers with an accepted WC claim may be eligible for partial wage replacement benefits (time loss) after 3 lost work days in WA and after 7 lost work days in OH. WA and OH are the largest 2 of only 4 states that have an exclusive State Fund—no private WC insurance companies operate in these states, which makes them particularly well-suited to population-based research. WC covers >97% of jobs covered by unemployment insurance in both states, and the share of all WC benefits paid by the two State Funds (vs. self-insurance) are very similar; 82% for OH and 78% for WA. The populations covered by the WA and OH WC programs are representative of gender, age, race, and ethnicity in the working populations in the two states.

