Aim 3 patient in-depth interviews. Patients who had an opioid prescription for at least 6 weeks paid for by WC or whose prescription payments have been reviewed in accordance with the state's ORP.

Exclusion Criteria

Aims 1, 2, & 3 (patient in-depth interviews only). Injured workers who are under 18 years of age.

Aims 1 & 2. Current cancer diagnosis and (for surveys only) non-English or -Spanish speakers, physically or mentally incapable of completing the survey, incarcerated, or deceased.

Aim 3. Non-English speakers.

Number of Study Groups/Cohorts

The primary analysis involves 2 groups/cohorts of injured workers, 1 from WA and 1 from OH. Secondary analyses involve two subgroups of injured workers within WA, defined by whether the injured worker's attending provider participates in Centers of Occupational Health and Education (COHE) care delivery.

Enrollment/Sample Size

Aims 1 & 2. The time series for Aim 1 will be based on data for all injured workers in OH and WA who file a new State Fund claim from January 1, 2010 through December 31, 2020. For the prospective cohort analysis, we anticipate including 4,636 eligible workers in WA and 779 in OH for a one-year cohort. Using WC claims, pharmacy billing data, and potentially prescription drug monitoring program (PDMP) data from each state, we will track opioid prescribing for each injured worker for a full year after date of injury. The worker survey will largely be drawn from this cohort, depending on the length of time needed to conduct an adequate number of surveys. All workers will be interviewed initially at 4-6 weeks

after injury (baseline). Workers who complete the baseline survey in the first year of recruitment will be asked to complete follow-up surveys at 6- and 12-months after injury. Workers who complete the baseline survey after the first year of recruitment will be asked to *only* do the 6-month follow-up survey due to time constraints. We anticipate that roughly 3,120 workers in WA and 525 workers in OH will complete baseline surveys. We anticipate roughly 1,700 completed 12-month outcome surveys from WA and 234 from OH.

Aim 3 key informants. No more than 12 interviews in WA, supplemented with policy documents to add detail. In OH, we will start with policy documents and use key informant interviews with individuals outside of BWC to complement and supplement the historical account.

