Aim 3 individual in-depth interviews. We will conduct 20-30 patient interviews and approximately 10 provider interviews in each state.

Sampling Method

Aims 1 & 2. Consecutive sampling. The entire eligible one-year cohort will be used for analyses based on administrative data, and consecutive sampling will be used to enroll survey participants from that cohort until target enrollment numbers are reached.

Aim 3 key informants. Purposive and snowball sampling. Potential key informants will be identified and invited to participate based on specific characteristics. Snowball sampling from these initial interviews will allow us to expand the sample until the body of interview data achieves theoretical saturation in each state.

Aim 3 individual in-depth interviews. Purposive and quota sampling. Potential interview participants will be identified and invited to participate based on specified characteristics until the body of interview data achieves theoretical saturation in each state. For provider interviews, we will also ask interviewed providers to recommend peers with experience prescribing opioids for WC patients (snowball sampling).

5. Exposures

The primary exposures of interest are the WC-based opioid review programs (ORPs) in each state: (1) prospective prior authorization (PA) with hard stops in WA, and (2) retrospective review (RR) with prescriber notification in OH. Secondarily, the COHE program is an exposure of interest, within WA only.

WA opioid review. Under WA regulatory procedures, payment for any opioid prescription billed beyond six weeks after the injury is denied unless the prescriber has submitted a checklist attesting to completion of all best practices from the regulations/guidelines. For example, the provider must document clinically meaningful improvement in pain and function during acute use. Thus, the WA intervention is prospective and includes a “hard stop” subject to an insurer’s decision based on regulatory authority.

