1	F. Subgroup response to opioid review decisions	Subgroup analysis using PDMP data	Opioids obtained from different prescriber or different payer	OH/WA cohorts
1	G. Describe usual care	Descriptives (rates)	Health care utilization	OH/WA cohorts
2	H. PA vs RR	GEE/propensity score & subgroup analysis	Secondary outcomes	OH/WA survey samples
2A	I. COHE vs non-COHE	GEE/propensity score & subgroup analysis	Unsafe opioid prescribing	WA cohort & survey sample
2A	J. COHE vs non-COHE	GEE/propensity score & subgroup analysis	Secondary outcomes	WA survey sample

Admin, administrative data; COHE, Centers of Occupational Health and Education; GEE, generalized estimating equations; ITSA, interrupted time series analysis; OH, Ohio; PA, prior authorization; RR, retrospective review; WA, Washington.

Aim 1

Specific aim 1. Examine the comparative effectiveness of prospective prior authorization (PA) with hard stops in WA versus retrospective review (RR) with prescriber notification in OH in reducing unsafe opioid prescribing.

Hypothesis 1. Prospective PA with hard stops (WA) will be associated with statistically significantly less unsafe opioid prescribing compared to RR and prescriber notification (OH). [See Analysis Topic B]

Aim 1. Analysis Topic A: Compare long-term prescribing patterns across states and identify discontinuities

This analysis will be based on a time series approach. We will construct data points for each month from January 1, 2010 through December 31, 2020. For each state, we will construct two separate time series. The first is the proportion of WC claims with any opioid prescription in the acute phase (0-6 weeks). The second is the proportion of WC claims with unsafe opioid prescribing (defined earlier) during the subacute phase (6-12 weeks). For each, calendar month denominators for the time series will be assigned based on date of injury, and numerators will be calculated for each one-month set of claims using the pharmacy billing data for up to three months after date of injury.

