This analysis is focused on the secondary and exploratory patient outcomes for this study, using administrative and survey data for the WA survey sample. Surveys will be conducted at approximately 6 weeks (baseline), 6 months, and 12 months after injury. Our estimates are rough and will be updated as survey enrollment proceeds. However, we anticipate that roughly 3,120 workers in WA will complete baseline surveys, that roughly 1,700 will completed 12-month outcome surveys, and that approximately half of those interviewed will have an attending provider affiliated with COHE.

This analysis will test Hypothesis 2A (stated above) with respect to patient outcomes, using parallel analyses to those described in Analysis Topic H. Most secondary and exploratory patient outcomes will be based on survey data, but several will be based on WC data (see Tables 2 and 3). The only adjustments to Analysis Topic H are that models will include only the WA survey sample, and the binary primary predictor and propensity score calculations will be based on COHE status rather than on state jurisdiction (1 for COHE, 0 for non-COHE).

Additional Information Relevant to Quantitative Analyses for Aims 1, 2, and 2A

Subgroups of Interest

Planned subgroup analyses are listed under the relevant analysis topics above. Because all subgroup analysis will be exploratory, non-exhaustive examples of potential subgroups have been specified. New subgroups of interest may be identified via exploratory data analysis and/or proposed ad hoc by the principal investigator, co-investigators, or stakeholders. The total number of subgroup analyses—and all subgroups and outcomes analyzed—will be reported, along with subgroup definitions and procedures used. If indicated, multiple comparisons will be accounted for using p-value adjustment.

Operational Definitions for Eligibility Criteria

These definitions will need to be aligned as much as possible across the two states. The following operational definitions are based on our history of working with WA WC data. They may need to be modified after preliminary OH WC data are available for inspection.

- Inclusion criteria:
 - New State Fund claim: Identified by each state WC agency
 - At least one opioid prescription during the first 6 weeks after date of injury: Based on WC pharmacy billing data
 - Ability to speak English or Spanish (for the survey only): This will be determined by interviewers during the contact/consent process
- Exclusion criteria:

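### Compensated time loss and opioid poisoning come from administrative data but are assigned to the survey samples, and no analysis topic carries out the full-cohort analysis that the Sampling Method section calls for

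*Combined protocol and SAP*

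**What the plan says.** Section 4 (Sampling Method) states that "The entire eligible one-year cohort will be used for analyses based on administrative data". Section 3 describes the design in the same spirit: "Aims 1 and 2 rely primarily on administrative data for a prospective cohort, with longitudinal surveys conducted among a subset of the cohort".

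Table 2 lists two secondary outcomes with an administrative source. Work status, measured by compensated time loss, comes from WC claims data at 6 weeks, 6 months and 12 months. Opioid poisoning comes from WC billing data at 12 months.

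The analysis text assigns the secondary outcomes to these samples:

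- Table 4 row H (Washington versus Ohio): "OH/WA survey samples".
- Table 4 row J (COHE versus non-COHE): "WA survey sample".
- Topic J: "This analysis is focused on the secondary and exploratory patient outcomes for this study, using administrative and survey data for the WA survey sample". It adds: "The only adjustments to Analysis Topic H are that models will include only the WA survey sample".
- Topic H notes that several outcomes come from WC data but names no separate sample for them. Its model adds baseline survey covariates to the Topic B set, and its propensity score is built from the combined list.

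Unsafe prescribing, the other administrative outcome, is handled differently. Topic B uses the full cohorts, Topic C repeats it in the survey subset as a sensitivity analysis, and Table 4 row I names "WA cohort & survey sample".

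**The concern.** Neither outcome needs an interview, and the plan already intends to obtain the claims and billing data for everyone in the cohorts. Limiting the analysis to survey respondents has three consequences.

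- Cohort members with usable outcomes are dropped.
- Survey non-response enters outcomes that are otherwise close to complete; the Missing Data section calls Washington administrative data virtually 100% complete and expects Ohio to be similar. That section also says contact details are largely complete for workers on WC benefits because the benefit requires them. Being reachable may therefore be related to time-loss status, which is the outcome. This is an inference, and the documents give no size or direction for it.
- The survey-only exclusions in Section 4 (language, incapacity, incarceration, death) carry over to outcomes for which they are not needed.

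With two texts pointing to different samples and no primary named, an analyst could defend either sample after seeing the results. Work disability is named in Aims 2 and 2A, and poisoning in Aim 2.

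**Working it through.** The documents give no power, effect size or event rate for these two outcomes, so there is no stated figure to reproduce. The check has a textual part and an arithmetical part.

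**Is there a full-cohort analysis anywhere?** Topic A covers prescribing time series. Topics B, C, D and I cover unsafe prescribing. Topics E and F cover review decisions and the response to them. Topic G describes health care utilization. H and J are the only topics for secondary outcomes, and their sample is the survey sample: explicitly in Table 4 and Topic J, by implication in the Topic H prose.

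**Inputs (Section 4, Enrollment/Sample Size; Topics H, I and J).** Cohort: 4,636 in Washington (WA), 779 in Ohio (OH). Baseline survey: 3,120 and 525. COHE share: about half of WA.

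**Unused cohort, if every respondent belongs to it.**
- WA: 4,636 − 3,120 = 1,516; 1,516/4,636 = 32.7%.
- OH: 779 − 525 = 254; 254/779 = 32.6%.

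Section 4 and Topic H allow survey accrual to run past the cohort. Each respondent from outside it leaves one more cohort member unused.

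**Standard error (SE) ratio, survey to cohort, unadjusted, independent workers, no trimming.**
- WA–OH: √[(1/3,120 + 1/525)/(1/4,636 + 1/779)] = 1.218.
- COHE, equal halves: √(4,636/3,120) = 1.219.

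**How the ratio moves** (trimming fractions of 10% and 20% are assumed):
- Only the cohort trimmed to common support, as Topic B plans: 1.218 × √0.9 = 1.16 and 1.218 × √0.8 = 1.09. It reaches 1 at about 33% trimmed.
- Only the survey sample trimmed, which Topic H allows if needed: 1.218/√0.9 = 1.28 and 1.218/√0.8 = 1.36.
- Equal trimming of both samples: unchanged.
- 1:1 matching on 525 OH respondents, also allowed by Topic H: √[(2/525)/(1/4,636 + 1/779)] = 1.59.
- COHE with provider clustering, at an assumed 5 patients per provider and an intraclass correlation (ICC) of 0.05: the cohort design effect is 1 + 4 × 0.05 = 1.20. In the survey sample the cluster size is 5 × 0.673 = 3.36 and the design effect is 1 + 2.36 × 0.05 = 1.118. The ratio is 1.219 × √(1.118/1.20) = 1.18.

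**95% half-widths for time loss**, 1.96 × √[p(1−p)(1/n₁ + 1/n₂)], at assumed proportions p of 20% and 50%, no trimming, in percentage points:
- WA–OH: 3.04 and 3.79 in the cohort; 3.70 and 4.62 in the survey sample.
- COHE: 2.30 and 2.88 in the cohort; 2.81 and 3.51 in the survey sample.

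These assume independent workers. Under the clustering assumed above, the COHE values widen by factors of √1.20 = 1.10 (cohort) and √1.118 = 1.06 (survey).

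**Expected OH poisoning events**, at assumed 12-month risks of 0.1% and 1%: 779 × risk = 0.78 and 7.79 in the cohort; 525 × risk = 0.53 and 5.25 in the survey sample.

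**The case against.** The best defence is that nothing conflicts. The Sampling Method sentence concerns analyses based on administrative data, whereas H and J mix administrative and survey data. Topic C also runs an administrative outcome in the survey subset, so the sentence cannot mean that every such outcome is always analysed only in the full cohort. This softens the contradiction. It does not supply the missing analysis: Topic C sits beside a full-cohort Topic B, and time loss and poisoning have no counterpart to B.

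The survey model also has a real advantage. It adjusts for baseline pain, function, mood, education, race/ethnicity and survey work status. That stands, and it is why neither sample is clearly better alone.

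The Missing Data section plans to compare respondents with non-respondents and to weight for non-response. This helps in part, but the weighting applies only if warranted, and it cannot represent groups excluded from the survey by design. Section 7 also calls the plan tentative pending Ohio data. That covers Ohio's data fields but does not explain Topic J, which uses Washington data alone.

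A reader might infer more than the text supports on three points:

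- *That the Topic H prose itself limits these outcomes to respondents.* It does not. The limit comes from Table 4 row H, a summary table, and from covariates that only respondents have.
- *That a third of the cohort and 22% of the SE are ceilings.* They are not. Accrual beyond the cohort, or trimming or matching the survey sample, makes them larger; trimming the cohort makes the SE ratio smaller.
- *That the survey-sample estimates are shown to be biased.* Selection is possible, but the documents do not allow its size or direction to be derived.

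**Conclusion.** The point holds as a gap between the plan's general rule and its specific topics. It is explicit for Topic J and Table 4 rows H and J, and implied for Topic H. Following the survey-sample text leaves about 33% of each cohort unused, or more if accrual runs past the cohort.

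The unadjusted SE is then about 1.22 times the full-cohort value, assuming independent workers and no trimming. Under the assumptions tried, the ratio ranges from about 1.09 to 1.59. The precision gain for Ohio poisoning is small, since very few events are expected in either sample. The case therefore rests mainly on time loss, on keeping survey selection out of outcomes that need no interview, and on fixing the primary sample in advance.

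A larger sample does not make time loss comparable between the states. Benefits start after 3 lost work days in Washington and 7 in Ohio (Section 4, Study Population and Setting). Only two secondary outcomes are affected; the primary analysis is not. The change should be made, but the study's main conclusion does not depend on it.

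**What to change.** - Reconcile the Sampling Method sentence with Table 4 rows H and J and with Topics H and J.
- Add full-cohort models of compensated time loss and opioid poisoning (both states for H, Washington for J), using the Topic B covariates and the planned clustering by attending provider.
- Keep the survey-sample models, with their survey covariates and propensity score, beside them.
- State in advance which is primary. The plan's own B/C structure would support the full cohort as primary with the survey model as sensitivity analysis, but the choice is the study team's.
- Report both estimates together, with the number trimmed for common support in each, and note the differing waiting periods when interpreting the Washington–Ohio time-loss result.

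The cost is a few text edits and a few extra models on data already planned for the full cohorts; Ohio completeness still has to be confirmed. The downside is that the full-cohort model lacks the survey confounders, so residual confounding may be larger there. Reporting both estimates shows how much the results differ but does not remove that confounding.

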OH opioid review. The OH regulations are similar to those in WA regarding best practices, but differ in approach. Rather than a “hard stop” on opioid prescription payments, an automated report identifies new opioid prescriptions beyond the acute phase. OH WC pharmacy and clinical staff review the medical record at 12 weeks to determine whether best practices were met. If not, the prescriber is notified via letter, and cases are reviewed again at 16 weeks. If best practices have still not been met, the prescriber

and worker are notified via letter that opioid coverage will end in 4 weeks. The OH program relies on retrospective chart review and communication of best practices to prescribers.

Centers of Occupational Health and Education (COHE) care delivery, in WA. The focus of the COHEs is to deliver occupational health best practices during the first 12 weeks after injury, during the transition from acute/subacute to chronic pain. The COHE delivery system has been developed over the past decade, and now approximately 50% of workers in WA receive care under these innovative arrangements. Critical elements of the COHE model include organizing care delivery on a population basis, high level executive health system support, ongoing care coordination by health service coordinators (HSCs), and stepped care management. Specific best practices include screening for psychosocial barriers to recovery using the validated Functional Recovery Questionnaire (FRQ); initiation of graded exercise; education regarding psychosocial barriers to recovery; and, more recently, a brief series of cognitive behavioral and reactivation techniques, i.e., activity coaching. COHE is a health care systems intervention, rather than a specific health care service or menu of services, that is primarily focused on improving the coordination of care at the health care community level, as well as with DLI. The COHE model consists of enhanced provider education regarding occupational health best practices and stepped-care features. Both usual care and COHE-based care in the WA workers' compensation (WC) system include the typical mix of health care services delivered for work-related injuries in Washington State, such as chiropractic care, physical therapy, evidence-based imaging services, and guideline-concordant surgery.

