 - Under 18 years of age: Age at injury, calculated as the difference between birthdate and date of injury

Operational Definitions for Key Covariates

Operational definitions will need to be aligned as much as possible across the two states. Thus, key covariates and their operational definitions will need to be determined after (1) preliminary OH WC data are available for inspection and (2) the survey is finalized with stakeholder input.

Clustering

Study objectives and the primary and secondary outcomes for Aims 1 and 2/2A pertain to the individual worker level. Multiple outcome measures for each worker (both administrative and survey based) require accounting for within-person correlation, which motivates the use of GEE. However, provider-level opioid prescribing patterns may induce intraclass correlation among injured workers treated by a particular provider. Each ORP decision is specific to an individual patient; however, providers either request PA in WA or are notified of RR in OH. These experiences may cause providers to adjust their practice for other patients in their care, impacting outcomes for provider-based patient clusters. The vast majority of providers prescribe opioids to very few WC patients. However, there may be some dependence of patient observations within the few higher-volume providers. Injured workers may have multiple prescribing providers over the course of a WC claim, which complicates cluster identification.

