The primary predictor for Aim 2A, COHE status, is assigned to injured workers based on provider-level COHE affiliation. COHE program features are determined at the WC system level but its effects may vary depending on provider adherence and individual worker circumstances. In order to obtain accurate standard errors and confidence intervals, we plan to specify models using robust standard error estimates and accounting for potential clustering by primary attending provider. This approach by necessity assumes person clusters are perfectly nested within attending provider clusters; however, attending provider can change over time. In practice such changes are uncommon in WA, and we are uncertain whether such changes can be tracked in OH. If feasible, we will assess clustering based on different approaches (e.g., first attending provider, attending provider in place for the longest period of time during the acute phase, or accounting for clustering only at the person level). We expect these approaches to yield similar results, but in the event they do not, we will proceed with the most conservative approach (highest standard errors).

Missing Data

Assumptions about the nature and prevalence of missing data made below will be assessed once preliminary WC and survey data sets are available. The administrative claims and pharmacy data are virtually 100% complete in WA; we will assess OH data when available, but expect similar completeness for all covariates associated with worker compensation or provider billing.

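### Clustering is planned on the attending provider and no prescriber definition is listed, so the standard error of the Washington–Ohio contrast on unsafe prescribing can be too small where the two providers differ

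*Combined protocol and SAP*

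**What the plan says.** Section 7, Clustering, explains why workers may not be independent: "provider-level opioid prescribing patterns may induce intraclass correlation among injured workers treated by a particular provider". It adds a spill-over route through the reviews: "These experiences may cause providers to adjust their practice for other patients in their care". It also names a difficulty: "Injured workers may have multiple prescribing providers over the course of a WC claim, which complicates cluster identification".

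Section 5 places both reviews on the prescriber. In Washington, payment beyond six weeks "is denied unless the prescriber has submitted a checklist attesting to completion of all best practices". In Ohio, records are checked at 12 weeks for best practices: "If not, the prescriber is notified via letter, and cases are reviewed again at 16 weeks".

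The primary outcome (Table 1; Analysis Topic B) is itself a measure of prescribing, over months 3 to 12.

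For the variance, section 7 plans robust standard errors "accounting for potential clustering by primary attending provider". If feasible, other approaches will be assessed; the examples are the first attending provider, the attending provider who served longest in the acute phase, and the person alone. If results differ, the approach with the largest standard error is used.

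The plan does not say that the attending provider is the prescriber, and it gives no figure for how often they coincide.

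**The concern.** A cluster-robust variance counts only the covariance between observations in the same declared cluster. Two workers with the same prescriber but different attending providers fall in different clusters, so any shared prescribing habit drops out of the standard error. State is a between-prescriber exposure (assuming prescribers rarely treat workers from both systems), so omitted positive correlation shortens the standard error of the state contrast.

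At stake is the interval and test for Hypothesis 1 on unsafe prescribing: Topic B, and its survey-sample sensitivity analysis, Topic C. The largest-standard-error rule is a sound safeguard, but it protects only across the approaches actually compared. As listed, these do not include the unit to which the plan attributes the correlation.

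**Working it through.** **No plan figure to reproduce.** The documents give no intraclass correlation (ICC), number of providers, workers per provider, or attending–prescriber overlap. The stated cohort sizes are 4,636 (WA) and 779 (OH), total 5,415. The plan's expectation of more than 3,000 clusters counts patients, not providers.

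**Which state matters most.** With equal outcome variance, Ohio's share of the variance of the unadjusted contrast is (1/779) / (1/779 + 1/4,636) = 4,636/5,415 = 0.86. Clustering missed in Ohio therefore passes almost fully into the interval.

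**Analytic check (all inputs assumed).** Let m be the worker-weighted mean number of workers per prescriber, and q the share of workers whose attending provider is also the prescriber. A pair sharing a prescriber is captured when both members match, with probability q².

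- True design effect = 1 + (m − 1) × ICC
- Captured design effect = 1 + q² × (m − 1) × ICC
- SE ratio = √(captured / true)
- Coverage of a nominal 95% interval = 2Φ(1.96 × ratio) − 1

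Example: m = 5, ICC = 0.05, q = 0.8. True = 1 + 4 × 0.05 = 1.20; captured = 1 + 0.64 × 4 × 0.05 = 1.128; ratio = √(1.128/1.20) = 0.970; coverage 94.3%.

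Ranges over ICC 0.01–0.10 and q 0.5–0.95:

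| m | SE ratio | Coverage |
|---|---|---|
| 2 | 0.965–1.000 | 94.2–95.0% |
| 5 | 0.886–0.998 | 91.8–95.0% |
| 10 | 0.803–0.996 | 88.4–94.9% |
| 20 | 0.713–0.992 | 83.8–94.8% |

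**Simulation (all inputs assumed except the cohort sizes).** Each setting had 1,500 runs with 4,636 and 779 workers, three binary windows averaged per worker, a normal prescriber effect on the logit scale, and a linear model for the state difference with cluster-robust SE. Non-matching attending providers were drawn at random within state. Small clusters give m of about 2.1. In the high-volume setting, 3% of prescribers have about 40 workers each, giving m of about 18. The ratio is attending-clustered SE over prescriber-clustered SE.

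| Clusters | Prescriber SD | q | SE ratio | Coverage, attending | Coverage, prescriber |
|---|---|---|---|---|---|
| Small | 0.5 | 0.5 | 0.984 | 95.3% | 95.5% |
| Small | 0.5 | 0.8 | 0.993 | 94.4% | 94.7% |
| Small | 1.0 | 0.5 | 0.947 | 93.5% | 94.9% |
| Small | 1.0 | 0.8 | 0.975 | 94.7% | 95.1% |
| High-volume | 0.5 | 0.5 | 0.849 | 90.0% | 94.0% |
| High-volume | 0.5 | 0.8 | 0.930 | 91.1% | 92.7% |
| High-volume | 1.0 | 0.5 | 0.697 | 79.8% | 91.9% |
| High-volume | 1.0 | 0.8 | 0.871 | 88.9% | 92.8% |

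The shortfall is about 1–5% with small clusters (0–4% analytically at m = 2) and about 7–30% with a high-volume tail. As q approaches 1, captured equals true and the shortfall is zero. With a few very large clusters, prescriber clustering also under-covers slightly.

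**The case against.** **The list of alternatives is open.** It is offered as examples and subject to feasibility, and section 7 calls much of the plan tentative until Ohio data arrive. Prescriber clustering is therefore not excluded. This stands: the gap is an uncommitted option, not a prohibition or an oversight, since the plan discusses multiple prescribers itself. But nothing commits the analysts to the comparison.

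**The attending provider is a reasonable proxy.** The plan speaks of workers treated by a provider and of patients in that provider's care. If the proxy is nearly perfect, nothing is lost. The documents neither show nor deny this.

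**Clusters are probably small.** Section 7 says nearly all providers write opioids for only a handful of these patients. That supports the lower end of the range. The same paragraph also allows for dependence within a few busier providers, so the upper end cannot be dismissed. Planned adjustment for provider type and specialty may remove some of the correlation; the calculations above do not model this.

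**The first prescriber is not the reviewed prescriber.** Every cohort member has an opioid fill in weeks 0–6, so a first prescriber exists, apart from same-day ties. But the reviews fall after six weeks (WA) or at 12 and 16 weeks (OH), and the primary outcome covers months 3–12. A reader might infer that a prescriber fixed at entry fully solves the problem of several prescribers per claim. It does not; it is an imperfect proxy that adds information.

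**Aim 2A is different.** COHE status is assigned through the attending provider, so clustering there matches the exposure. A worker's prescriber can differ from the attending provider, so COHE status need not be constant within prescriber. The formulas above then do not apply.

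**Conclusion.** The mismatch is real for the Washington–Ohio contrast on unsafe prescribing, and its direction is clear: any positive prescriber correlation that attending-provider clusters miss makes the standard error too small. Its size cannot be fixed from the documents. Under the assumptions above it is about 0–5% if prescribers have about two workers each, and about 7–30%, with coverage of about 80–91%, in the simulated case of a few high-volume prescribers and incomplete overlap. It vanishes if attending provider and prescriber nearly always coincide.

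A reader might go further and infer that the nominal 5% test really runs at about 10%. That figure follows from √(1 + (m − 1) × ICC) = √(1 + 9 × 0.05) = 1.20 and 2 × (1 − Φ(1.96/1.20)) = 0.10. It requires m = 10, ICC = 0.05 and attending-provider clusters that capture none of the correlation. The documents support none of these, so it is at most a bound for those inputs. Nor should it, or the ratios above, be carried to Hypothesis 2A. The point bears less on survey outcomes than on prescribing outcomes.

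**What to change.** In section 7, Clustering, add an opioid-prescriber definition to the approaches compared for the prescribing outcomes: for example the prescriber of the first qualifying fill, or the main acute-phase prescriber, with a tie rule for same-day fills. Apply the existing largest-standard-error rule to the enlarged set. Keep attending-provider clustering in the set; the prescriber definition supplements it. If a few prescriber clusters prove very large, consider a small-sample correction.

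Report, by state, the number and size of prescriber clusters and how often prescriber and attending provider coincide. This also shows whether the plan's expectation of similar results is borne out.

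For Aim 2A keep attending-provider clustering; two-way clustering with prescriber is an optional sensitivity analysis.

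The change depends on prescriber identity being available, which is plausible but unconfirmed. Appendix A lists pharmacy billing and provider information, section 8 recruits prescribers from agency lists, and Ohio writes to prescribers. Prescriber (DEA) numbers are mentioned only for the monitoring-program data, whose feasibility was still being confirmed. The cost is one or two further variance estimates, more programming if two-way clustering is used, and intervals that stay the same or widen.
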